1. ABSTRACT

Atrial fibrillation (AF) is a common, morbid condition. Anticoagulation to prevent thromboembolic strokes is a foremost priority in AF but adherence is challenging for patients and lapses in anticoagulation are common. Chronic disease self-management (CDSM) is a recognized program to enhance self-efficacy and improve adherence, quality of life, and patient-centered health outcomes. Rural patients with AF experience increased vulnerability to adverse outcomes due to geographic and social isolation, poor health care access, and limited health literacy. Study team will conduct a single-center parallel group randomized clinical trial to test the efficacy of a relational agent to improve patient-centered care in AF delivered by smartphone. The Principal Investigator and study team have used the agent - a computer character that simulates face-toface conversation using voice, hand gesture and gaze cues to provide education, monitoring and problem-solving - to improve health behaviors and outcomes in individuals with limited computer and health literacy. Here, the team will expand its successful 30-day relational agent pilot to develop a novel CDSM program for AF. This study will combine the relational agent with the AliveCor Kardia smartphone heart rate and rhythm monitor. The team will implement a 4-month CDSM curriculum and assess its sustainability at 8 and 12 months. The trial randomizes 264 patients with AF who are receiving anticoagulation for stroke prevention to (1) the relational agent and Kardia intervention, accompanied by provider alerts for prespecified results; or (2) the control, consisting of an AF educational session and a smartphone with a general health application (WebMD). Our aims are: (1) To assess the effect of the relational agent and Kardia intervention on anticoagulant adherence, as determined by the proportion of days covered (PDC), and selfreport. (2) To identify the effect of the intervention on health care utilization, hospitalizations, emergency visits, and AF-related procedures at 1-year follow up. (3) To determine the effect of the intervention on the patient-centered outcomes of quality of life and symptoms, as measured by the AF Effect on QualiTy of life (AFEQT) measure, specific to AF, and the general Patient-Reported Outcomes Measurement Information System-29 Profile at baseline, 4, 8 and 12 months. (4) To examine mechanisms for the effect of the intervention by symptom burden, AF classification, health literacy and intervention use. The trial will additionally follow the cohort through the study period for exploratory analyses of rurality and outcomes associated with AF. Expected Results: In this project we will evaluate a scalable patient-centered intervention to improve anticoagulation adherence, health care utilization and patient-centered outcomes in vulnerable rural individuals with chronic AF. If proven successful, this intervention can be broadly disseminated to improve the care of patients with AF.

BACKGROUND

Standard care is insufficient to address the combined challenges of AF, its complex symptoms and treatments, and the social determinant and health literacy obstacles that exacerbate outcomes with the condition. This study team has developed a novel, practical mHealth intervention that is accessible to high-risk patients such as those with limited social resources or health literacy.

2. STUDY RATIONALE AND SIGNIFICANCE OF THE RESEARCH

- a) AF prevalence is estimated to reach 12 million US adults by 2030.^{1,2} AF increases risks of stroke 5-fold,³ heart failure 3-fold,^{4,5} dementia 2-fold,^{6,7} and death 1.5- to 2-fold.⁸ Individuals with AF have 4.7-times greater annual days of hospitalization than those without,⁹ and expenditures for Medicine beneficiaries with AF have increased 1.6-fold since 1999.¹⁰ Among Medicare beneficiaries, the mortality rate following a diagnosis of AF is 19.5% at 1 year and 48.8% at 5 years.¹¹ Even on optimal therapy, patients experience a stroke rate of 1.5%, heart failure of 4-5%, and mortality of 3% per year.¹² This project aims to reduce the morbidity and social costs of AF.
- b) Poor medication adherence results from the complex interaction between patients, their social environment, and the health care system and professionals.¹³ Patient-level barriers to adherence have been characterized as limited health literacy and behavioral obstacles to successful medication management.¹⁴ Rural individuals have additional risk for poor adherence because of limited health literacy, lower social resources, poverty, and geographic distance from care providers.^{15,16} They also experience disparities in cardiovascular outcomes, attributable in part to social determinants of health.^{17,18} Rural regions have higher unemployment and poverty rates, lower educational attainment,¹⁹ higher rates of low health literacy, less access to health care services,²⁰ and worse control of cardiovascular disease and AF risk factors (hypertension, obesity, diabetes).^{21,22} Our program promotes longitudinal, patient-centered strategies for rural patients to overcome adherence challenges.²³

R01AG028669, 1R01HL081307, NCI 5R21CA127511, R01HL116448). The agent speaks with synthetic speech accompanied by animation to provide health education, empathic counseling, and monitoring. The patient engages by listening to didactic content or questions and selecting responses on the touch screen. Patients converse with the agent, develop an empathic therapeutic alliance, and report/record across domains of CDSM. The relational agent (a) elicits symptoms and (b) gestures to enhance educational content. The intervention here integrates the relational agent with the AliveCor Kardia (Mountain View, CA) smartphone heart rate and rhythm monitor to guide Kardia use and enhance CDSM in AF.

f) Our relational agent/Kardia intervention improves the current paradigm for rural AF care²⁴ by aiming to: (1) Enhance patient-centered resources. AF is a complex condition that requires long-term patient engagement³¹⁻³⁴ and the relational agent serves as an empathic coach to improve the patient experience of this chronic disease. We provide a non-pharmacologic, non-invasive approach that is accessible to patients, patient-centered, and disease-specific. (2) Synergize the relational agent/Kardia. Relational agent content prompts use of the Kardia when users report symptoms. The relational agent can correlate symptoms with heart rate and rhythm, improve symptom characterization, and guide CDSM to improve multiple patient-centered domains assessed by the Patient-Reported Outcomes Measurement Information System (PROMIS) instrument used here.³⁵ (3) Increase health-related attention. Rural individuals often have less access to resources for adherence support and disease-specific education.³⁶ Patients will benefit from AF-specific education, symptom monitoring, self-management content, and encouragement of engagement and activation.

3.0 STUDY AIMS

3.1 Aim 1

To assess the effect of the relational agent/Kardia intervention on anticoagulant adherence. We will quantify adherence to anticoagulation with (a) proportion of days covered (PDC) obtained from pharmacy data, and (b) self-report, at 4, 8, and 12 months. Hypothesis: Intervention participants will have better anticoagulant adherence than control arm participants as measured by objective and self-reported assessments of adherence.

3.2 Aim 2

To identify the effect of the intervention on health care utilization (HCU). We will quantify 12month HCU for intervention administration. Hypothesis: Intervention participants will have lower HCU events compared to control arm participants.

3.3 Aim 3

To determine the effect of the intervention on HRQoL and symptoms. We will compare HRQoL and symptoms between the intervention and control arms at 4, 8, and 12 months with the AF Effect on QualiTy of life (AFEQT) instrument (specific to HRQoL in AF) and the Patient-Reported Outcomes Measurement Information System (PROMIS)-29 Profile. Hypothesis:

Intervention participants will have superior HRQoL and lower symptom burden compared to control arm participants at 4, 8, and 12 months.

3.4 Aim 4

To examine mechanisms for the effect of the intervention. We will determine how patientcentered baseline factors including sex, race, health literacy, AF classification (paroxysmal versus chronic), and symptom burden moderate the intervention effect, and how intervention engagement and use, change in symptom burden, and AF therapies mediate the intervention effect on our primary and secondary outcomes.

4. STUDY DESIGN

4.1 Study Overview

This is a randomized clinical trial to evaluate the effect of a smartphone-based intervention on health outcomes in people with the heart disease called atrial fibrillation. The study will enroll 264 patients residing in rural municipalities (defined as "rural" by the Center for Medicaid and Medicare Services Rural Health Clinics Program) with this condition and randomize them to the intervention or control. Intervention participants will receive a smartphone with an application (or app) called a relational agent, which simulates conversation. In addition, they will receive an AliveCor Kardia for heart rate and rhythm monitoring, an FDA-approved, widely used instrument that pairs with the smartphone. Control participants will receive a smartphone with a general health application (WebMD) and they will not receive an AliveCor Kardia device. The intervention will last 4 months and participants will have visits at baseline, 4, 8 and 12 months. The study will evaluate the improvement in quality of life, medical adherence and health care utilization resulting from the intervention.

5.0 STATISTICAL CONSIDERATIONS

We propose a two-arm RCT to evaluate the efficacy of the relational agent and AliveCor Kardia heart rhythm monitor to improve patient-centered outcomes in patients with the debilitating chronic condition atrial fibrillation (AF). We will recruit 264 patients with AF receiving anticoagulation over a 30-month period, prioritizing recruitment in socioeconomically depressed regions in rural Northwest Pennsylvania. We will randomize participants 1:1 to receive the mobile relational agent and Kardia (n=132) or control (n=132) for 4 months, conducting randomization with a web-based data management system that we have used in prior RCTs. Randomization will be stratified by type of oral anticoagulant (warfarin or direct acting oral anticoagulant). We will assess the impact of our intervention at 4, 8 months and then at 12 months to determine sustainability. Our primary hypothesis will test whether the relational agent and Kardia intervention can improve adherence to anticoagulation as quantified by the PDC and by participant self- report. Our secondary hypotheses will evaluate 1) assessments of health care utilization between the intervention and control; 2) the improvement in health-related quality of life at 4, 8, and 12 months compared to the control, as measured by instruments specific to AF and general, validated quality of life assessments; and 3) the mechanisms for the effect of the intervention, as evaluated by assessments of moderation and mediation. All participants will have return visits at 4, 8, and 12 months. The outcomes will all be calculated without reference to intervention arm. We will use the intention-to-treat principle for all primary and secondary analysis. All analyses will be blinded to trial randomization arm.

Statistical approach for Aim 1. The primary outcome for Aim 1 is anticoagulant adherence as assessed by PDC. We will use the intention-to-treat principle for all primary and secondary

analyses. We will analyze PDC as continuous (range 0-1, higher ratio indicating better adherence) and binary (optimally adherent if ≥0.8) variables. We will assess differences between the 2 study arms in PDC at 12 months with linear regression (for continuous PDC) or logistic regression (for binary PDC) adjusting for trial stratification factor (as suggested by Kahan and Morris³⁷). We will conduct our secondary assessments of adherence at 4 8, and 12 months similarly. We will categorize individuals scoring ≥ 2 on any of the 3 self-report adherence items (range 1-5, Voils et al.³⁸) as nonadherent. To assess whether the effect of the intervention changes over time, we will use linear (for continuous measures) or non-linear (for categorical measures) mixed-effect models with random intercepts with adherence measures modeled as a function of study arm, study visit and their interaction. We calculated the statistical power to detect a range of difference in PDC (our primary outcome) between the intervention and control arms. After accounting for 10% attrition through 12 months (consistent with our prior RCTs), we determined that a sample size of 119 in each study arm will enable us to detect a minimum difference in PDC between the two groups as small as 11.7% with 85% power (assuming a SD=30%). Our power calculations assume use of 2-sided tests with 0.05 significance level. With an additional, unexpected 10% attrition (n=106 per arm, to accommodate for relocation, loss-to- follow-up, institutionalization, or death), we will be able to detect a minimum difference in PDC as small as 12.4% (0.41 standardized mean difference) with 85% power. Both are considered small effect sizes per Cohen's guidelines.³⁹

Statistical approach for Aim 2. We will compare HCU across trial arms in models that again account for trial stratification factor.³⁷ We will use the electronic health record (EHR) in concert with 4-, 8-, and 12-month self-report to catalog events (hospitalization, emergency room and ambulatory visits, medications, and procedures) and classify them as related to AF. We will determine person-year of follow-up as starting from the date of randomization to the 12-month visit. We will then classify HCU in aggregate and by item as count outcomes. We will use generalized estimating equations (GEE) negative binomial regression models (chosen instead of Poisson regression due to expected over-dispersion in the data). Similar approaches will be used to assess counts for each HCU component. Based on preliminary data from an outpatient registry of individuals with chronic AF, we expect there will be 42.0 events for every 100 person-years in the control arm of the trial.⁴⁰We estimate that we have 85% power to detect a minimum absolute reduction of 21 events per 100 person-years in the intervention group, assuming an equivalent number of events in the control group at 12 months with a sample size of 132 per arm. A 20% attrition in study participation (n=106 per arm) at 12 months will still allow us to detect a minimum of absolute reduction of 23 events per 100 person-years in the intervention group with 85% statistical power. As exploratory analyses, we will perform survival analyses to compare the time to event between the intervention and control arms for preselected outcomes: AF-related hospitalization, emergency visit, or procedure; myocardial infarction; heart failure; stroke; and allcause mortality. Participants will contribute 18 to 51 months of follow-up: those without the event of interest will be censored at the end of follow-up. We will examine the assumption of proportional hazards and use Cox regression models to estimate the hazards ratio for assigned treatment for each outcome.

Statistical approach for Aim 3. We estimate that patients randomized to our intervention will have a clinically relevant improvement in HRQoL as demonstrated by AFEQT global score at 4-months follow-up vs. control. Our demonstration cohort (N=31) had a mean increase in AFEQT global score of 12±16 (from 64±23 to 76±19) over 30 days (range 0-100, greater scores indicating superior HRQoL). We will use linear regression adjusted for trial stratification factors and the baseline score as per Harrell⁴¹ to evaluate the differences in AFEQT global and domain-specific scores between study arms at 4 months. We will similarly assess the effect of the intervention for

each of the 4 AFEQT domains and the 8 symptom and HRQoL domains measured by the PROMIS-29 at 4 months. Next, we will assess sustainability of the intervention effect at 8 and 12 months using linear mixed models. Our power calculations assume a 90% 4-month assessment completion rate (to accommodate for 10% attrition), 2-tailed α =0.05, and standard deviation of 17 (representing the upper limit of the 95% confidence interval for the SD and consistent with the data used to determine the minimum important difference⁴²). Based on these assumptions, we expect our sample size (119 per arm) will enable us to detect a minimum difference in AFEQT between the two study arms at 4 months of at least 6.3, corresponding to 0.37 SD, a small effect size.³⁹ A 20% sample size attrition (n=106 per arm) at 12 months will allow us to detect a difference in AFEQT of at least 0.41 SD.

Statistical approach for Aim 4. Subgroup analyses will be performed to assess moderation of the intervention effect by baseline patient-centered factors: (1) sex; (2) race (white vs non-white); (2) health literacy, assessed using the Newest Vital Sign (NVS); (3) AF classification (paroxysmal vs permanent), (4) symptom burden, measured by the AFEQT; (5) anticoagulant type (warfarin or direct oral anticoagulant (**DOAC**)); (6) self-reported anticoagulant nonadherence (<2 or \geq 2); and (7) duration of anticoagulation (<1 or \geq 1 year). We will formally test for effect modification by creating a regression model for each outcome including the subgroup variable, the intervention assignment and the interaction between the subgroup variable and intervention and evaluating the significance of the interaction term. The false discovery rate⁴³ will be used to adjust for multiple comparisons. Causal mediation analyses will be used to determine the degree to which intermediate patient-level factors explain the intervention effect as potential mediators of the primary and secondary outcomes.⁴⁴⁻⁴⁶ We will estimate the direct and indirect effects of the intervention on outcomes accounting for (1) changes in symptom burden during follow-up, measured by the AFEQT: (2) introduction of new AF therapies over 12-month study participation (antiarrhythmic, cardioversion or electrophysiologic study); (3) relational agent and Kardia usage; and (4) EHR alerts. Instead of emphasizing p-values, we will focus on estimation of mediation effect sizes.

Race and sex. We will ensure our study cohort is 50% women and 30% non-white race, of whom 80% (24% overall) will be black race. (1) We have reviewed⁴⁷ AF is less prevalent in blacks⁴⁸⁻⁵⁰ but associated with worse outcomes⁵⁴ (2) Women have worse HRQoL and increased stroke risk than men.⁵¹⁻⁵³ (3) We have developed strategies to oversample participants of black race and female sex. Although the current trial is not specifically design to assess racial/sex variability in the intervention effect, since the overall effect has not yet been established, subgroups analyses among all race/sex groups will set the stage for further studies that focus on racial/sex effects. We note our statistical power for such trial participation: (1) if we randomize 64 study participants of black race, then we will have 85% power to detect a 22.8% PDC difference between trial arms. (2) Similarly, if we randomize 135 women, 51% of trial participants, then we will have 85% power to detect a 15.6% difference between trial arms.

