8. STUDY PROCEDURES

8.1 Assessments

Study team will conduct research assessments with each study subject at baseline, and then at 4, 8 and 12 month follow up visits. Sociodemographic, clinical and outcome information will be obtained directly from subjects and through review of their medical records including hospital databases, outpatient records, and insurance records. Study team will administer the assessments as portrayed in table below.

Table 1

Assessment	Screening/	Baseline	4mth Follow-up	8mth Follow-up	12mth Follow-up	Role to assessment
(In order of study procurement)	Consent (in clinic	(in clinic or	(in clinic or	(by phone)	(by phone)	
	or by phone)	by phone)	by phone)			
Clinic Screening Form (includes 6-item screener)	Х					
Consent	Х					
Sociodemographic Characteristics						Exploratory Outcome
Demographics		Х				
Transportation		х				
Kaiser: Your Current Living Situation		x				
Smoking		x				
Alcohol Use		x				
Montreal Cognitive Assessment		Х			Х	
Quality of Life Assessment						Secondary Outcome
AFEQT		Х	Х	Х	Х	
PROMIS-29 Profile v2.0		Х	Х	Х	Х	
Anticoagulant Adherence						Primary Outcome
VOILS: Medication Nonadherence		Х	Х	Х	Х	
VOILS: Medication - Reasons for nonadherence		Х	Х	Х	Х	
Self-Efficacy						Exploratory Outcome
PROMIS Self-Efficacy for Managing Medications & Treatments		Х	Х	Х	х	
PROMIS Self-Efficacy Managing Symptoms		Х	Х	Х	Х	
Social Measures						Exploratory Outcome
BRIEF Health Literacy Screener		Х				. ,
Newest Vital Sign (NSV)		Х				
Connor-Davidson Resilience Scale (CD-RISC-10)			Х			
Berkman-Syme Social Network Index			Х			
Psychiatric Symptoms						Covariate
Patient Health Questionnaire (PHQ-8)		X	Х	Х	Х	
Medical Co-Morbidity Variables						Covariate
AF History		Х				
Vital Signs (BMI)		Х				
Antiarrhythmic Medications		Х	Х	Х	Х	
Other Medications		Х				
Other Medical History		Х				
New AF Therapies (Cardioversion, pacemaker)			X	X	X	
Proportion of Days Covered (PDC)					X	Primary Outcome
Health care utilization (events)			Х	Х	Х	Secondary Outcome
RELATIONAL AGENT/Kardia Information						Exploratory Outcome
Relational Agent usage			Х			
Study team Kardia review time			Х			
AliveCor Tracking			Х			
Satisfaction in using Relational Agent and Kardia			Х			
Cardiac hospitalizations (heart failure myocardial infarction			v	N N		
hospitalization for AF)			X	X	x	
AS NEEDED FORMS:			1			
Adverse Event and Serious Adverse Event monitoring						
Protocol Deviations						
Unanticipated Problems						
Withdrawal						

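### The Aim 1 regressions leave out the baseline self-report adherence score: a modest gain in precision goes unused, clearest for self-report and possibly negligible for PDC

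*Combined protocol and SAP*

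**What the plan says.** All references are to the combined protocol and SAP.

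- **Section 5.0, Aim 1.** The 12-month PDC comparison uses "linear regression (for continuous PDC) or logistic regression (for binary PDC) adjusting for trial stratification factor". Anticoagulant type is the only stratification factor. The plan then states: "We will conduct our secondary assessments of adherence at 4 8, and 12 months similarly". A patient counts as nonadherent on scoring 2 or more "on any of the 3 self-report adherence items (range 1-5").
- **Section 3.1.** Aim 1 measures adherence by "proportion of days covered (PDC) obtained from pharmacy data, and (b) self-report, at 4, 8, and 12 months". The primary hypothesis in section 5.0 is likewise that the intervention can "improve adherence to anticoagulation as quantified by the PDC and by participant self- report".
- **Section 8.1, Table 1.** The row "VOILS: Medication Nonadherence" is marked at baseline, 4, 8 and 12 months. The PDC row is marked at 12 months only.
- **Section 5.0, Aim 4.** Baseline "self-reported anticoagulant nonadherence", split at 2, is listed as a moderator.
- **Section 5.0, Aim 3.** The 4-month AFEQT comparison uses "linear regression adjusted for trial stratification factors and the baseline score".

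**The concern.** The plan treats two repeated patient-reported measures differently and gives no reason. AFEQT is adjusted for its own baseline; self-reported adherence is not, although its baseline is collected on the same instrument and is thought important enough to be a moderator. A baseline score that predicts the outcome removes variance from the treatment comparison, so leaving it out gives up power that costs nothing to collect.

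The comparison with Aim 3 applies to self-report only. PDC has no baseline value, so for PDC the baseline self-report score would be a related covariate from a different instrument, and how well it predicts PDC is unknown. Precision is what is at stake; neither bias nor the validity of the primary test is in question.

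**Working it through.** **1. The plan's own figures.** Inputs from section 5.0: SD 30 points, two-sided 0.05, 85% power, 119 per arm (132 × 0.9 = 118.8) or 106 (132 × 0.8 = 105.6). The normal approximation for the detectable difference is (1.960 + 1.036) × 30 × √(2/n), which gives 11.65 at 119 and 12.35 at 106. With the noncentral t the results are 11.70 and 12.40, matching the plan. The stated power therefore uses no covariate and does not depend on the point made here.

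**2. PDC with the baseline covariate.** Residual SD = 30 × √(1 − r²), where r is the assumed correlation of baseline self-report with PDC. Noncentral t, continuous PDC:

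| r | Detectable difference, 119 per arm | Detectable difference, 106 per arm | Power at 11.7 points, 119 per arm |
|---|---|---|---|
| 0 | 11.70 | 12.40 | 85.0% |
| 0.1 | 11.64 | 12.34 | 85.3% |
| 0.2 | 11.46 | 12.15 | 86.4% |
| 0.3 | 11.16 | 11.83 | 88.1% |
| 0.4 | 10.72 | 11.37 | 90.5% |
| 0.5 | 10.13 | 10.74 | 93.3% |

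At r = 0.1 to 0.2 the gain is 0.06 to 0.24 points.

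**3. Self-report by simulation.** Known inputs: 119 per arm, three items scored 1–5, outcome = any item at 2 or above. Assumed inputs:
- control nonadherence of 40% or 50% and a true difference of 18 points;
- inter-item latent correlation of 0.5, 0.7 or 0.9;
- baseline-to-follow-up latent correlation (rho) of 0.3, 0.5 or 0.7;
- 30% of patients in one stratum, unrelated to outcome.

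There were 4,000 trials per setting. The logistic model with stratum alone was compared with stratum plus the mean of the three baseline items. Power without and with the covariate:

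| Control rate, inter-item correlation | rho 0.3 | rho 0.5 | rho 0.7 |
|---|---|---|---|
| 40%, 0.5 | 85.7 → 85.9 | 86.2 → 87.6 | 85.7 → 88.7 |
| 40%, 0.7 | 85.4 → 86.2 | 86.1 → 88.6 | 85.2 → 90.4 |
| 40%, 0.9 | 84.8 → 86.4 | 85.4 → 88.7 | 84.9 → 92.8 |
| 50%, 0.5 | 81.6 → 82.5 | 80.6 → 82.6 | 80.7 → 84.8 |
| 50%, 0.7 | 81.1 → 82.1 | 81.5 → 84.4 | 80.6 → 87.8 |
| 50%, 0.9 | 82.9 → 84.4 | 80.8 → 84.7 | 79.9 → 89.3 |

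The gains are 0.2–1.6, 1.4–3.9 and 3.0–9.4 percentage points. The variance of the standardised risk difference falls by 1–4%, 4–11% and 8–26%. Rejection under the null was 4.2–5.8% with the covariate and 4.5–6.0% without. Repeating the simulation at inter-item correlation 0.7 gave gains of about 0.4–0.7, 1.6–3.3 and 6.3–7.3 points, within or close to these ranges.

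**4. A simpler model.** With one binary baseline measure, control nonadherence of 30% or 50%, and correlation 0.3 to 0.5 on the observed 0/1 scale, power rises from about 85–86% to about 88–94% (variance ratio about 0.92 to 0.75). A correlation on the observed scale is not the latent correlation of step 3, so the figures are not interchangeable. The direction agrees.

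**5. Missing baseline scores.** With 10% missing at random (assumed) and inter-item correlation 0.7, power at 40% / 50% control nonadherence is:

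| Handling | rho 0.3 | rho 0.5 | rho 0.7 |
|---|---|---|---|
| No baseline covariate | 85.7 / 81.3 | 84.9 / 80.9 | 85.1 / 80.4 |
| Covariate, mean imputed | 86.2 / 82.1 | 87.5 / 83.9 | 90.3 / 86.3 |
| Covariate, complete cases | 81.8 / 76.9 | 84.3 / 80.0 | 87.4 / 83.4 |

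At rho 0.3 and 0.5, dropping patients with no baseline score is worse than not adjusting.

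**6. Effect measure.** For 40% against 22%, the odds ratio with no baseline covariate is (0.22/0.78) / (0.40/0.60) = 0.42. Conditional on the baseline score (inter-item correlation 0.7) it becomes about 0.40, 0.38 and 0.35 at rho 0.3, 0.5 and 0.7, while the risk difference stays at 18 points.

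**The case against.** Stratum-only adjustment is a complete, prespecified choice that respects the randomisation, and a further prognostic covariate is optional. The only powered outcome is PDC, which is where the gain may be nil. No self-report regression is written out; the omission is read from the statement that the secondary assessments are done in the same way. The Aim 1 mixed model may already use the baseline response, because section 4.1 counts baseline among the visits. Every input to the size of the gain is assumed. The simulation is also noisy: one power estimate near 85% has a standard error of √(0.85 × 0.15 / 4,000) = 0.6 points, and power without the covariate drifts from 82.9% to 79.9% across one row although it should not depend on rho.

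Much of this stands as a limit on size. The plan contains no error, the smallest gains are within simulation noise, and the 9.4-point maximum starts from a low reference value. It does not remove the point. The natural reading of the text is that self-report follows the stratum-only form. The mixed model addresses change in effect over time and does not replace the per-visit regressions, and the text does not say whether baseline is one of its visits. Adding the covariate to the PDC model does no harm once missing values are imputed.

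**Conclusion.** The concern holds as a missed efficiency. The Aim 1 regressions name only the anticoagulant stratum, a same-instrument baseline exists for self-report, and Aim 3 already follows the better practice. For self-report, the gain is small at a latent correlation of 0.3, a few points of power at 0.5, and 3.0–9.4 points at 0.7. For PDC it is 0.3 to 1.4 points of power at r = 0.1 to 0.2, and matters only if baseline self-report tracks pharmacy refills better than that. The correlations, nonadherence rates, effect size and missingness are all assumptions, so the direction is firm and the size is not. The primary test and its stated power are unaffected. The change is worth making because it is nearly free, but the trial does not depend on it.

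**What to change.** In the Aim 1 section of the SAP:

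- Add the baseline self-report score as a covariate beside anticoagulant stratum in the self-report regressions, and in the PDC regressions with the note that the gain there may be small.
- State its form, for example the mean of the three items, which keeps more information than the split at 2 used in Aim 4.
- State that missing baseline scores are singly imputed, for example with the overall baseline mean ignoring arm, so that every randomised patient with an outcome stays in the analysis.
- For binary outcomes, report a standardised risk difference beside the odds ratio, because the odds ratio becomes conditional on the covariate.
- As a minor clarification, confirm in one sentence that the stratum also enters the Aim 1 and Aim 3 mixed models, and the Aim 4 moderation models where it is not already the subgroup variable.

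The cost is a few sentences, with no new form, visit or patient. The change alters prespecified models, and section 7.6 leaves staff and participants unblinded, so it must be dated and fixed before any outcome is seen by arm.
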